NCT03596723

Study ID:
KPI-121-C-010

Study Title:
Safety and Efficacy of KPI-121 1% Ophthalmic Suspension Versus Prednisolone
Acetate Ophthalmic Suspension 1% for the Treatment of Inflammation Following
Cataract Surgery in Children 0 to 3 Years of Age

Date:
11 Jul 2018

KALA PHARMACEUTICALS, INC.
Clinical Protocol KPI-121-C-010

Project: KPI-121

Compound Number/Name: KPI-121 1%

Protocol Number: KPI-121-C-010

Protocol Title: Safety and Efficacy of KPI-121 1% Ophthalmic Suspension versus Prednisolone Acetate Ophthalmic Suspension 1% for the Treatment of Inflammation Following Cataract Surgery in Children 0 to 3 Years of Age

Sponsor: Kala Pharmaceuticals, Inc.
[name]
[name]

Medical Monitor: 

Issue Date: Original: 14 Nov 2017
Amendment 1: 19 Dec 2017
Amendment 2: 16 Mar 2018
Amendment 3: 11 Jul 2018

Approved by: 

KALA PHARMACEUTICALS, INC.
Clinical Protocol KPI-121-C-010
Investigator Signature Page

Project: KPI-121

Compound Number/Name: KPI-121 1%

Protocol Number: KPI-121-C-010

Protocol Title: Safety and Efficacy of KPI-121 1% Ophthalmic Suspension versus Prednisolone Acetate Ophthalmic Suspension 1% for the Treatment of Inflammation Following Cataract Surgery in Children 0 to 3 Years of Age

Sponsor: Kala Pharmaceuticals, Inc.
[name]
[name]

Issue Date: Original: 14 Nov 2017
Amendment 1: 19 Dec 2017
Amendment 2: 16 Mar 2018
Amendment 3: 11 Jul 2018

For Serious Adverse Event Reporting: 

For Serious Adverse Event Questions: 

Investigator Name (printed or typed):

Investigator's Signature:

_____ Date

SYNOPSIS

Study Title:	Safety and Efficacy of KPI-121 1% Ophthalmic Suspension versus Prednisolone Acetate Ophthalmic Suspension 1% for the Treatment of Inflammation Following Cataract Surgery in Children 0 to 3 Years of Age
Objectives:	To compare the safety and efficacy of KPI-121 1% ophthalmic suspension (KPI-121 1%) dosed twice daily versus prednisolone acetate ophthalmic suspension 1% (prednisolone acetate 1%) dosed four times daily in children 0 to 3 years of age following cataract surgery.
Study Population:	The study population will consist of pediatric subjects from 0 through 3 years of age who have undergone routine, uncomplicated cataract surgery.
Number of Subjects:	Approximately 120 subjects who are candidates for cataract surgery will be screened. One study eye from approximately 60 subjects will be randomized.
Investigational Products:	KPI-121 1% and vehicle or prednisolone acetate 1% will be supplied as investigational product.
Route and Duration of Administration:	Subjects will be randomized to either: 
 • 1-2 drops of KPI-121 1% and vehicle dosed two times per day each for a total of four times per day (QID) instilled in the study eye for 29 days \pm 2 days post-surgery, starting at the first post-operative assessment. This may be followed by treatment or taper using a commercially available product as determined by the Investigator. 
OR
 
 • 1-2 drops of prednisolone acetate 1% dosed QID instilled in the study eye for 29 days \pm 2 days post-surgery, at the first post-operative assessment. This may be followed by treatment or taper using a commercially available product as determined by the Investigator.
Study Design:	This is a Phase 3B, multicenter, double-masked, randomized, parallel-group, active-controlled study designed to evaluate the safety and efficacy of KPI-121 1% versus prednisolone acetate 1% in controlling postoperative inflammation in children 0 to 3 years of age who have undergone cataract surgery. Approximately 120 subjects who are candidates for cataract surgery will be screened.

Subjects who meet all eligibility criteria and undergo routine, uncomplicated, cataract surgery will be randomized into this study at approximately 20 centers located in the United States (US).

Subjects will be randomized into one of two study groups in an approximate 1:1 ratio. Subjects will be randomized to either:

- **BOTH** KPI-121 1% ophthalmic suspension **AND** KPI-121 vehicle dosed BID each for 29 days \pm 2 OR
- Prednisolone acetate ophthalmic suspension 1% dosed QID for 29 days \pm 2 days.

Dosing with investigational product will be initiated at the first post-operative assessment and will be instilled as one to two drops in the surgery eye according to the assigned dosing regimen for 29 \pm 2 days. This may be followed by treatment or taper using a commercially available product as determined by the Investigator. This study will include 6 clinic visits as well as the surgery visit over 35 to 53 days total study duration. Visit 1 (Screening) will occur between 14 and 1 day(s) prior to surgery. Subjects who meet preoperative screening inclusion/exclusion criteria will be entered into the study. On the day of surgery, subjects will undergo routine cataract surgery according to the Investigator's normal procedures. At the first post-surgery assessment, which may be later on the same day of surgery or the following day, eligibility regarding inclusion and exclusion criteria will be confirmed and subjects will be randomized to one of the two treatment arms. The first dose of investigational product will be administered in the clinic, and parents/guardians will be instructed how to dose and record investigational product use. This will be considered Day 1 (Visit 2). Following randomization, subjects' parents/caregivers will be instructed to return to the clinic to be evaluated on Day 8 \pm 2 days (Visit 3), Day 15 \pm 2 days (Visit 4), Day 29 \pm 2 days (Visit 5), and Day 36 \pm 2 days (Visit 6). Additional investigational product will be dispensed at Visit 4. Investigational product will be discontinued at Visit 5. Used investigational product kits will be collected by the study staff at Visits 4 and 5. At Visit 5 further treatment or taper with a commercially available product may be given as determined by the Investigator. Additionally, a phone contact will be made between Visits 4 and 5 (Day 21-23) to assess subject progress. Subjects will return for a Follow-Up/Safety Visit on Day 36 \pm 2 days (Visit 6).

	
Assessments in this study will include (when obtainable):
 
 • Medical History Review • Age Appropriate Visual Acuity (VA) • Signs of anterior chamber ocular inflammation – cell and flare grading, corneal clarity, conjunctival injection, chemosis, hypopyon as well as vitritis and wound integrity • Symptoms of anterior ocular inflammation – photophobia and lacrimation • Intraocular Pressure (IOP) Measurement • Dilated Ophthalmoscopy • Modified Global Assessment of Postoperative Inflammation • Rescue Therapy Assessment • Assessment of Concomitant Medication Use • Assessment of Adverse Events (AEs) • Dosing Compliance Assessment/Dosing Diary Review
Efficacy Evaluation:	
Primary Efficacy Evaluation:
 
 1. The proportion of study eyes with anterior chamber cell grade = 0 at Visit 4 (Day 15 ± 2 days) without receiving rescue medication prior to Visit 4 as compared between the KPI-121 1% dose BID and the prednisolone acetate 1% dosed QID treatment arms. 
Secondary Efficacy Evaluation:
 
 1. The proportion of study eyes with a Modified Global Overall Assessment of Postoperative Inflammation Score = 0 at Visit 4 (Day 15 ± 2 days) without receiving rescue medication prior to Visit 4 as compared between the KPI-121 1% BID and the prednisolone acetate 1% QID treatment arms. 
Statistical Analysis:
 
The efficacy and safety analyses will be based on a single study eye for each subject. Each subject's study eye will be defined as the surgery eye. All statistical analyses will be performed using Statistical Analysis System (SAS) software.

	
The primary analysis population will be the Intent-to-Treat (ITT) population, defined as all subjects randomized and with at least one post-baseline assessment. A subset of efficacy analyses, the Per Protocol (PP) population, will be repeated using data from those subjects who were randomized, completed 15 days \pm 2 days of investigational product use, had complete data at Visit 4 (Day 15 \pm 2 days), and did not have significant protocol deviations. Rescued subjects will be included in the PP population if they did not have significant protocol deviations: however, these subjects will be considered treatment failures.
 
No inferential statistical analyses are planned. Data will be summarized using descriptive statistics only. Assessment of efficacy will be based primarily on the number and percentage of subjects in each treatment group with an anterior chamber cell grade of 0 at Visit 4 (Day 15 \pm 2 days) with no need for rescue medication through Visit 4 and, secondarily, on the Modified Global Overall Assessment of Postoperative Inflammation score of 0 at Visit 4 (Day 15 \pm 2 days) without receiving rescue medication prior to Visit 4.
 
The individual components of the Global Assessment score will also be evaluated (i.e., number and percentage of subjects in each treatment group in each score category at each visit).

Safety Evaluations:	
Assessment of AEs
 
Change from baseline to each post-surgery visit in ocular signs:
 
 • Visual Acuity • IOP Measurement • Dilated Ophthalmoscopy (at Visits 1 and 5 only) 
Assessment of safety will be based on the assessment of AEs. To allow for at least a 95% chance of detecting an AE with a 10% incidence rate, a minimum sample size of 30 subjects per group (KPI-121 1% or prednisolone acetate 1%) is required.

Eligibility Criteria:	
Inclusion Criteria:
 
At Visit 1, individuals of either gender and any race will be eligible for study participation if they:

1. Have informed consent and Health Insurance Portability and Accountability Act (HIPAA) authorization provided by parent or guardian prior to any study-related procedures.
2. Are 0-3 years of age (have not had their 4th birthday) as of the date of surgery.
3. Are candidates for routine, uncomplicated, cataract surgery
 - a. With or without capsulotomy and vitrectomy
 - b. With or without posterior chamber intraocular lens (IOL) implantation
 - c. But not combined with any other surgery.
4. Have a unilateral cataract or have bilateral cataracts and are candidates for surgery:
 - a. On the first eye, and surgery on the second eye is not planned until after the subject completes participation in the study **OR**
 - b. On the second eye, and surgery on the first eye was uncomplicated, any post-operative inflammation has resolved and anterior chamber cell and flare grades both = 0.

Exclusion Criteria:

In order for subjects to be eligible at Visit 1 they may not:

1. Have a post-traumatic cataract.
2. Have suspected permanent low vision or blindness in the fellow non-study eye.
3. Have active uveitis in either eye.
4. Have an ocular neoplasm in either eye.
5. Have the presence of any active or suspected viral, bacterial, or fungal disease in the either eye.
6. Have a history of glaucoma, ocular hypertension, steroid-induced IOP rise or have an IOP >21 mmHg in either eye at the screening or randomization visit(s).
7. Require the use of any topical ophthalmic medication in the study eye within 2 days prior to surgery and for the duration of the study, except for drops that are needed to examine the eye or to prepare for and undergo surgery as well as post-operative antibiotic drops. **NOTE:** Besifloxacin Ophthalmic Suspension is not permitted within 2 days prior to surgery or for the duration of the study.

8. Require the use of systemic or ocular non-steroidal anti-inflammatory drugs within 2 days prior to surgery and for the duration of the study.
9. Require treatment with systemic, inhaled, or ocular corticosteroids within 14 days prior to surgery and for the duration of the study with the exception of intraoperative ocular corticosteroids.
10. Require a change in use of nutraceuticals or multivitamins within 2 days prior to surgery and for the duration of the study.
11. Have known hypersensitivity or contraindication to the investigational product(s) or their components.
12. Have a diagnosis of:
 - a) Severe/serious ocular condition that in the judgment of the Investigator could confound study assessments or limit compliance.
 - b) Severe/serious systemic disease or uncontrolled medical condition that in the judgment of the Investigator could confound study assessments or limit compliance.
13. Have been exposed to an investigational product within 30 days prior to surgery.

Randomization Criteria:

Pred Forte[®] (prednisolone acetate ophthalmic suspension, USP) 1%, an approved glucocorticoid product, will be purchased and supplied to sites as the active comparator product. Pred Forte[®] contains prednisolone acetate (microfine suspension) 1% as the active ingredient. Inactive ingredients are benzalkonium chloride (as preservative); boric acid; edetate disodium; hypromellose; polysorbate 80; purified water; sodium bisulfite; sodium chloride; and sodium citrate. The pH during its shelf life ranges from 5.0 - 6.0.

For additional details on toxicology studies and the respective safety profiles, see the KPI-121 Investigator's Brochure and the Pred Forte[®] package insert.

1.2. JUSTIFICATION FOR ROUTE OF ADMINISTRATION AND DOSE SELECTION

KPI-121 1% and prednisolone acetate 1% will be administered as topical ophthalmic suspensions. Direct instillation into the eye is the most efficient method for delivery to the ocular surface and is an accepted and widely used method for topical application to the eye. KPI-121 1% dosed BID has been shown to be safe and effective in adults (Kim, Gupta, Holland and Brazzell, 2018). Prednisolone acetate 1% dosed QID has been shown to be safe and effective in both adults and children (Wilson, 2016).

1.3. GCP COMPLIANCE

This clinical trial will be conducted in compliance with the protocol, International Conference on Harmonization (ICH) guidelines, Good Clinical Practices (GCP) guidelines and other applicable regulatory requirements.

1.4. POPULATION TO BE STUDIED

Approximately 120 subjects, from 0 - 3 years of age, who are candidates for cataract surgery will be screened. The surgical/study eye from approximately 60 subjects who have undergone routine, uncomplicated, cataract surgery, with or without capsulotomy and vitrectomy and with or without posterior chamber intraocular lens (IOL) implantation, but not combined with any other surgery, will be randomized and evaluated at approximately 20 centers located in the US.

2. TRIAL OBJECTIVES AND PURPOSE

2.1. OBJECTIVE

The primary objective of this study is to investigate the safety and efficacy of KPI-121 1% ophthalmic suspension given BID compared to prednisolone acetate ophthalmic suspension 1% given QID in pediatric subjects who have undergone routine, uncomplicated cataract surgery.

3. TRIAL DESIGN**3.1. PRIMARY EFFICACY EVALUATION**

The primary efficacy evaluation is the proportion of study eyes with anterior chamber cell grade = 0 at Visit 4 (Day 15 ± 2 days) without receiving rescue medication prior to Visit 4 as compared between the KPI-121 1% dosed BID and the prednisolone acetate 1% dosed QID treatment arms.

3.2. SECONDARY EFFICACY EVALUATION

The secondary efficacy evaluation is the proportion of study eyes with a Modified Global Overall Assessment of Postoperative Inflammation Score = 0 at Visit 4 (Day 15 ± 2 days) without receiving rescue medication prior to Visit 4 as compared between the KPI-121 1% BID and the prednisolone acetate 1% QID treatment arms.

3.3. SAFETY ENDPOINTS

Safety evaluations will include:

- Assessment of AEs
- Visual Acuity
- IOP Measurement
- Dilated Ophthalmoscopy (assessed at visits 1 and 5 only)

Ocular assessments will be summarized at each post-surgery and compared between the KPI-121 1% dosed BID and the prednisolone acetate 1% dosed QID treatment arms.

3.4. DESCRIPTION OF TRIAL DESIGN

This is a Phase 3B, multicenter, double-masked, randomized, parallel-group, active-controlled study designed to evaluate the safety and efficacy of KPI-121 1% versus prednisolone acetate 1% in pediatric subjects who undergo cataract surgery. Approximately 120 subjects, from 0 - 3 years of age, who are candidates for cataract surgery will be screened. Approximately 60 subjects, after undergoing routine, uncomplicated, cataract surgery, will be randomized into this study at approximately 20 centers located in the US.

Subjects who meet all eligibility criteria will be randomized to one of two treatment arms in an approximate 1:1 ratio:

- KPI-121 1% BID **AND** vehicle BID, to support the masking of the investigational product
- Prednisolone acetate 1% QID

Dosing of investigational product will be initiated at the first post-surgery assessment, Visit 2 (Day 1), instilled as 1-2 drops in the study eye. The first dose of investigational product will be administered by the subject's parent/caregiver under the supervision of a dedicated dosing coordinator who is otherwise uninvolved in the assessment or evaluation of the subject.

This study will include up to 6 clinic study visits and a phone contact and 35 to 53 days total study duration. Visit 1 (Screening) will occur between 14 and 1 day(s) prior to surgery and subjects who meet preoperative screening inclusion/exclusion criteria will be entered into the study. On the day of Surgery, subjects will undergo routine cataract surgery according to the Investigator's normal procedures. The first post-surgery assessment, which may be later on the same day of surgery or the following day will be considered Visit 2 (Day 1). At this visit, subjects who continue to meet the eligibility criteria will be randomized to one of the two study groups and will initiate dosing with investigational product. Following randomization, the subject's parent/caregiver will be instructed to instill investigational product in the study eye four times a day (QID) for 29 days \pm 2 days up until Visit 5. The subject will return to the clinic to be evaluated at Visit 3 (Day 8 \pm 2 days), Visit 4 (Day 15 \pm 2 days) and Visit 5 (Day 29 \pm 2 days/End of Investigational Product Use Visit). A phone contact will be made between Visits 4 and 5 (Day 21 -23) to assess subject progress.

Investigational product will be discontinued and collected at Visit 5. This may be followed by treatment or taper using a commercially available product as determined by the Investigator. Subjects will return for a follow up visit, Visit 6 (Day 36 \pm 2 days) then will be released from the study.

A summary of events is provided in [Appendix 1](#). Assessments in this study will include (when obtainable):

- Medical History Review
- Visual Acuity, (Snellen, Optotype recognition, Central/Steady/Maintained with Fix and Follow or Fix and Follow alone per the subject's age and as determined by the Investigator and used for all study visits for the subject) ([Appendix 2](#))
- Signs of anterior ocular inflammation – cell and flare grading, corneal clarity, conjunctival injection, chemosis, hypopyon, as well as vitritis and wound integrity, (Slit lamp biomicroscopy, ophthalmoscopy or light examination depending on subject's tolerance. The method used for these

assessments will be determined by Investigator and used for all study visits for the subject) ([Appendix 3](#))

- Symptoms of anterior ocular inflammation – photophobia and lacrimation
- IOP Measurement ([Appendix 4](#))
- Dilated Ophthalmoscopy ([Appendix 5](#))
- Modified Global Overall Assessment of Postoperative Inflammation ([Appendix 6](#))
- Rescue Therapy Assessment
- Concomitant Medication Use Assessment
- Assessment of Adverse Events
- Dosing Compliance Assessment/Dosing Diary Review ([Appendix 7](#))

A study schematic follows ([Figure 1](#)).

FIGURE 1: STUDY SCHEMATIC

Screening	Surgery	Treatment KPI-121 1% Ophthalmic Suspension + KPI-121 vehicle (30 Subjects)					Follow-Up
		Treatment Prednisolone Acetate 1% Ophthalmic Suspension (30 Subjects)					
Visit 1	Cataract Surgery	Visit 2 Day 1 (day of surgery or following day)	Visit 3 Day 8 ± 2 days	Visit 4 Day 15 ± 2 days	Phone Contact Day 21-23 days	Visit 5 Day 29 ± 2 days	Visit 6 Day 36 ± 2 days
-14 to -1 days prior to surgery		Randomization	Treatment	Treatment	Treatment	End of IP Use	Off Study
No Dosing	No Dosing	First use of IP QID Dosing	QID Dosing	QID Dosing	QID Dosing	Last Dosing	No Dosing

3.4.1. Investigational Product

KPI-121 1% ophthalmic suspension is a sterile, aqueous, submicron suspension of loteprednol etabonate (LE). Each mL of KPI-121 1% ophthalmic suspension contains 10 mg of LE as the active ingredient. [REDACTED]

[REDACTED]

KPI-121 1% ophthalmic suspension will be supplied in a white, low-density polyethylene (LDPE) bottle with a controlled-drop, linear low-density polyethylene tip and a pink, high-density polyethylene cap. The dropper bottle also has a white LDPE tamper-evident overcap which, when removed, exposes the pink screw cap for opening the bottle and dispensing the product. KPI-121 1% is supplied as a minimum fill of 2.8 mL in a 5-mL bottle.

KPI-121 vehicle will be supplied in the same type of bottle/tip/cap configuration and will contain all components at the concentrations used in the KPI-121 1% ophthalmic suspension with the exception of the active component, LE.

TABLE 1: COMPOSITION OF KPI-121 1.0% (w/v) INVESTIGATIONAL PRODUCT

Ingredient	Function	Concentration (% w/v)
Loteprednol etabonate	Active pharmaceutical ingredient	1.0
[REDACTED]	[REDACTED]	[REDACTED]
[REDACTED]	[REDACTED]	[REDACTED]
[REDACTED]	[REDACTED]	[REDACTED]
[REDACTED]	[REDACTED]	[REDACTED]
[REDACTED]	[REDACTED]	[REDACTED]
[REDACTED]	[REDACTED]	[REDACTED]

TABLE 2: COMPOSITION OF KPI-121 VEHICLE

Ingredient	Function	Concentration (% w/v)
[REDACTED]	[REDACTED]	[REDACTED]
[REDACTED]	[REDACTED]	[REDACTED]
[REDACTED]	[REDACTED]	[REDACTED]
[REDACTED]	[REDACTED]	[REDACTED]
[REDACTED]	[REDACTED]	[REDACTED]
[REDACTED]	[REDACTED]	[REDACTED]
[REDACTED]	[REDACTED]	[REDACTED]

Pred Forte[®] (prednisolone acetate ophthalmic suspension, USP) 1% contains the active ingredient prednisolone acetate (microfine suspension) 1%. Other ingredients include benzalkonium chloride as a preservative; boric acid; edetate disodium; hypromellose; polysorbate 80; purified water; sodium bisulfite; sodium chloride; and sodium citrate. The exact concentrations of excipients are unpublished. The pH during its shelf life ranges from 5.0 - 6.0.

Pred Forte[®] (prednisolone acetate ophthalmic suspension, USP) 1% will be supplied as 1 ml of sterile aqueous suspension in opaque white 5 mL LDPE plastic dropper bottles with white, high impact polystyrene caps. The commercial bottle label will be over-wrapped to cover the commercial label, and then a masked clinical trial label will be applied to the overwrap. masked clinical trial label.

Subjects' parents/caregivers will be instructed to shake the investigational product bottle well before every use.

The randomized investigational product kits to be dispensed will consist of a box with four dropper bottles, labeled Bottle 1 through Bottle 4.

At Visit 2, eligible subjects' parents/caregivers will receive an investigational product kit containing four bottles. Parents/caregivers will be instructed to dose with 1-2 drops of Bottle 1 in the morning, followed by 1-2 drops of Bottle 2 at midday, 1-2 drops of Bottle 3 in the afternoon, and 1-2 drops of Bottle 4 at bedtime. This treatment schedule will be followed for 29 days \pm 2 days. All bottles should be stored upright and shaken well before dosing.

Subjects randomized to KPI-121 1% will receive investigational product kits containing both KPI-121 1% (Bottles 1 and 4) and vehicle (Bottles 2 and 3). Thus, the treatment schedule will result in QID dosing with 2 of the doses KPI-121 1% and 2 of the doses vehicle.

Subjects randomized to prednisolone acetate 1% will receive kits with 4 bottles of prednisolone acetate 1%, for QID dosing.

Subject's parent/caregiver will return their kits (and bottles) and receive a new kit containing the same product at Visit 4 to ensure sufficient investigational product through Visit 5. At Visit 5 they will return their second kit and end investigational product use. Completion of investigational product use may be followed by treatment or taper with a commercially available product as determined by the Investigator.

All kit labels and dropper bottle labels will contain the following information: sponsor name, protocol and kit number, storage temperature, and required statement(s) per the appropriate regulatory agency. The dropper bottle labels will also be printed with the bottle number (e.g., Bottle 1, Bottle 2, etc.).

Subjects' parents/caregivers will be instructed to shake the investigational product bottle well prior to administering each dose. When subjects receive the first dose administered in the clinic, the dose will count as one of the daily doses. Parents/caregivers will then administer the additional doses of investigational product later that day, according to the dosing schedule and instructions provided by the dosing coordinator.

The Investigator will store all investigational product upright in a secure area, with limited access, at controlled room temperature (15-25°C/59 -77°F). Parents/caregivers will be instructed to store the investigational product upright at room temperature.

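### At the permitted 2 drops per dose, the stated 1 mL comparator fill lasts to Visit 4 only if drops are small, whereas the KPI-121 1% fill has a wide margin

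*Combined protocol and SAP*

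**What the plan says.** Section 3.4.1 gives two fill volumes. The comparator "will be supplied as 1 ml of sterile aqueous suspension in opaque white 5 mL LDPE plastic dropper bottles". For the test product, "KPI-121 1% is supplied as a minimum fill of 2.8 mL in a 5-mL bottle". For the vehicle it gives only the container: "KPI-121 vehicle will be supplied in the same type of bottle/tip/cap configuration". No vehicle fill is stated.

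The same section ties each bottle to one time of day: caregivers are to "dose with 1-2 drops of Bottle 1 in the morning, followed by 1-2 drops of Bottle 2 at midday", with Bottle 3 in the afternoon and Bottle 4 at bedtime. In the comparator arm, "Subjects randomized to prednisolone acetate 1% will receive kits with 4 bottles of prednisolone acetate 1%, for QID dosing". In the test arm the kit holds "KPI-121 1% (Bottles 1 and 4) and vehicle (Bottles 2 and 3").

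One kit is allocated at Visit 2 (Section 6.1). Caregivers then "receive a new kit containing the same product at Visit 4 to ensure sufficient investigational product through Visit 5", and Section 5.1.5 confirms that the first kit is collected and the second dispensed at Visit 4 (Day 15 ± 2). No earlier resupply is described. Visit 4 is also the primary efficacy time point (Section 3.1).

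**The concern.** The second kit is justified by sufficiency of supply, so the plan recognises supply as a constraint. Yet it gives no drop volume, no overfill for the comparator and no days-of-supply calculation. The stated active fills differ 2.8-fold (2.8 / 1), although every bottle in both arms is used at the same rate.

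If a first-kit comparator bottle ran out, the missed doses would fall in the days just before the primary assessment. The success rate in that arm might then fall, either directly or through discretionary rescue, which counts as failure (Section 5.4). Some comparator subjects might also leave the per-protocol set, which requires 15 ± 2 days of product use (Sections 9.1.2 and 9.6). With about 30 subjects per arm and descriptive analysis only, one subject moves an arm's rate by 1/30 = 3.3 percentage points. The diary in Appendix 7 records date, time and number of drops, so an empty bottle would look the same as a caregiver's omission.

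**Working it through.** The plan has no supply figure to reproduce, so the check is a per-bottle calculation.

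**Inputs from the documents.** Comparator fill is 1000 µL and KPI-121 1% fill is at least 2800 µL. Each bottle is used once a day at 1 or 2 drops (all Section 3.4.1). The first kit runs from Day 1 to Visit 4, Day 13 to Day 17 (Section 5.1.5).

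**Uses per bottle before exchange.** With Visit 4 on Day 15, a bottle is used 15 times if that day's dose comes from the first kit, and 14 times if it comes from the second. With Visit 4 on Day 17, the maximum is 17 uses.

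**Assumptions.** Drop volume is not in the documents; 30, 40 and 50 µL are shown as an assumed range. No spillage or repeat drops are counted, and the whole stated fill is taken as deliverable.

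**Break-even drop volume** = fill / (drops per dose × uses). A bottle runs out early if its drops are larger than this. At 2 drops per dose:

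| Uses | Drops needed | Comparator, 1000 µL | KPI-121 1%, 2800 µL |
|---|---|---|---|
| 13 | 26 | 38.5 µL | 107.7 µL |
| 14 | 28 | 35.7 µL | 100.0 µL |
| 15 | 30 | 33.3 µL | 93.3 µL |
| 17 | 34 | 29.4 µL | 82.4 µL |

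At 1 drop per dose the comparator thresholds double: 1000/15 = 66.7 µL and 1000/17 = 58.8 µL.

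**Full 2-drop doses per bottle** = whole drops in the fill, divided by 2 and rounded down:

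| Assumed drop | Comparator | KPI-121 1% |
|---|---|---|
| 30 µL | 33 drops, 16 doses | 93 drops, 46 doses |
| 40 µL | 25 drops, 12 doses | 70 drops, 35 doses |
| 50 µL | 20 drops, 10 doses | 56 drops, 28 doses |

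So at 30 µL the comparator passes Day 15 but falls short of a 17th dose (34 × 30 µL = 1.02 mL). At 40 µL it is finished after Day 12, and at 50 µL after Day 10. At 1 drop per dose the same bottle lasts 33, 25 or 20 days, longer than any first-kit interval.

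**Where the arms separate.** At 2 drops per dose, for drops of about 36 to 82 µL, a comparator bottle is empty before nominal Day 15 while a KPI-121 1% bottle lasts even to Day 17.

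**Per-protocol set.** Taking the lower limit of 15 ± 2 as 13 days, supply fails to cover it only above 1000/26 = 38.5 µL. Between 35.7 and 38.5 µL, a bottle can be short of Day 15 and still cover 13 days.

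**Second kit.** If Visit 4 is on Day 13 and Visit 5 on Day 31, each bottle may be used 19 times: 1000/38 = 26.3 µL at 2 drops. This falls after the primary time point and bears only on later exposure.

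**The case against.** The strongest reply is that the documents contain no contradiction. Fill, drop instruction and exchange interval conflict only once a drop volume is supplied, and a shortage also needs 2 drops at most doses for two weeks. At 30 µL the bottle passes nominal Day 15. The fills are also different kinds of figure: one is a minimum fill, and the other describes a purchased commercial product whose overfill and tip output are unknown. All of this stands, so the finding has to be conditional.

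A reader might infer that only the comparator arm can run out of product. The documents do not support that. Half the bottles in a KPI-121 kit are vehicle, whose fill is not stated. The asymmetry is shown for active bottles only, although a vehicle shortage would not reduce active dosing.

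A reader might also infer that KPI-121 would be made to look better. Nothing in the documents quantifies the effect of missing the last few days of dosing on a cell grade of 0, so that direction is plausible but not demonstrated.

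Monitoring is partly in place. The diary captures every dose and its drops, compliance is reviewed at Visit 3, a dosing coordinator outside the masked assessment team handles product and diary (Section 3.4.2), and unscheduled visits are possible (Section 5.1.9). Missed doses could already be counted by arm. What is missing is the reason for a missed dose and a plan to tabulate it.

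**Conclusion.** The concern holds conditionally. Following the plan at a drop number it permits can exhaust the comparator's active product shortly before the primary assessment if drops exceed about 33-36 µL (29 µL at Day 17). The KPI-121 1% bottles reach the same point only above about 93-100 µL (82 µL at Day 17). Across the assumed 30-50 µL range at 2 drops, the shortfall runs from none at nominal Day 15 to about five days (15 − 10). At 1 drop there is none.

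This rests on an assumed drop volume, near-constant use of 2 drops, no waste, and 1 mL being the true deliverable fill. Spilled or repeated drops would lower the thresholds; overfill would raise them. The two bottle types may also deliver different drop sizes, so each threshold should be read against its own bottle. A lower comparator success rate, and loss of comparator subjects from the per-protocol set above 38.5 µL, are possible consequences and not established ones. The point deserves action because the check is cheap and the exposure among active bottles is one-sided.

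**What to change.** - Reconcile the stated comparator fill with the drop instruction and the kit-exchange interval (Sections 3.4.1 and 5.1.5).
- Confirm whether 1 mL is the intended fill and how many drops a comparator bottle actually delivers. State the vehicle fill.
- Ensure that the supplied volume covers the maximum use the instructions already permit up to each kit exchange, handled identically in both arms so that masking is kept.
- Add an empty bottle as a recorded reason for a missed dose, and tabulate missed doses before Visit 4 by arm.

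The cost is a supply check, possibly more product per kit, and one extra field at diary review. No change to the dose or the number of drops is proposed.
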